## 8.3.12 Medication Error, Drug Abuse, and Drug Misuse

#### **8.3.12.1** Timelines

If an event of medication error, drug abuse, or drug misuse occurs during the study, then the investigator or other site personnel informs the appropriate AstraZeneca representatives within **1 calendar day**, ie, immediately but **no later than 24 hours** of when they become aware of it.

The designated AstraZeneca representative works with the investigator to ensure that all relevant information is completed within 1 (Initial Fatal/Life-Threatening or follow up

Fatal/Life-Threatening) or 5 (other serious initial and follow up) calendar days if there is an SAE associated with the medication error, drug abuse, or misuse (Section 8.3.9) and within 30 days for all other medication errors.

#### **8.3.12.2** Medication Error

For the purposes of this clinical study, a medication error is an **unintended** failure or mistake in the treatment process for an IMP or AstraZeneca NIMP that either causes harm to the participant or has the potential to cause harm to the participant.

The full definition of medication error can be found in Appendix B 4.

#### **8.3.12.3 Drug Abuse**

Drug abuse is the persistent or sporadic **intentional**, non-therapeutic excessive use of IMP or AstraZeneca NIMP for a perceived reward or desired non-therapeutic effect.

The full definition of drug abuse can be found in Appendix B 4.

#### **8.3.12.4 Drug Misuse**

Drug misuse is the **intentional** and inappropriate use (by a study participant) of IMP or AstraZeneca NIMP for medicinal purposes outside of the authorized product information, or for unauthorized IMPs or AstraZeneca NIMPs, outside the intended use as specified in the protocol and includes deliberate administration of the product by the wrong route.

The full definition of drug misuse can be found in Appendix B 4.

#### 8.3.12.5 Reporting of Overdose

Refer to Section 6.8 for definition and treatment of overdose.

- An overdose with associated AEs is recorded as the AE diagnoses/symptoms on the relevant AE modules in the eCRF and on the Overdose eCRF module.
- An overdose without associated symptoms is only reported on the Overdose eCRF module.

If an overdose on an IMP or AstraZeneca NIMP occurs in the course of the study, the investigator or other site personnel inform appropriate AstraZeneca representatives immediately, but **no later than 24 hours** of when he or she becomes aware of it.

The designated AstraZeneca representative works with the investigator to ensure that all relevant information is provided to the AstraZeneca Patient Safety data entry site within 1 or 5 calendar days for overdoses associated with an SAE (Section 8.3.9) and within 30 days for all other overdoses.

#### **8.3.13** Medical Device Deficiencies

As described in Section 6.1.2, third-party medical devices will be supplied under the study protocol.

In this study any deficiency observed with a third-party medical device will be collected and reported to the manufacturer.

A medical device deficiency is an inadequacy of a medical device with respect to its identity, quality, durability, reliability, safety, or performance. Medical device deficiencies include malfunctions, use errors, and information supplied by the manufacturer.

The AstraZeneca medical device complaint report will be used to collect the deficiency.

# 8.4 Human Biological Samples

Instructions for the collection and handling of biological samples will be provided in the study specific laboratory manual. Samples should be stored in a secure storage space with adequate measures to protect confidentiality. For further details on Handling of Human Biological Samples refer to Appendix C.

Samples will be stored for a maximum of 15 years from the date of the issue of the CSR in line with consent and local requirements, after which they will be destroyed/repatriated.

- PK samples will be disposed of after the Bioanalytical Report finalization or 6 months after issuance of the draft Bioanalytical Report (whichever is earlier), unless consented for future analyses.
  - PK samples may be disposed of or anonymized by pooling. Additional analyses may be conducted on the anonymized, pooled PK samples to further evaluate and validate the analytical method. Any results from such analyses may be reported separately from the CSR.
- Remaining ADA sample aliquots will be retained at AstraZeneca or its designee for a
  maximum of 15 years following issue of the CSR. Additional use includes but is not
  limited to further characterization of any ADAs, confirmation and/or requalification of
  the assay as well as additional assay development work. The results from future analysis
  will not be reported in the CSR.

#### **8.4.1** Pharmacokinetics

- Plasma samples will be collected for measurement of concentrations of cotadutide as specified in Section 1.3.
- Samples may be collected at additional time points during the study if warranted and agreed upon between the investigator and the sponsor, eg, for safety reasons. The timing

of sampling may be altered during the course of the study based on newly available data (eg, to obtain data closer to the time of peak or trough matrix concentrations) to ensure appropriate monitoring.

- Plasma samples will be used to analyze the PK of cotadutide. Samples collected for analyses of cotadutide plasma concentration may also be used to evaluate safety or efficacy aspects related to concerns arising during or after the study.
- Samples will be collected, labeled, stored, and shipped as detailed in the Laboratory Manual.

## **Determination of Drug Concentration**

Samples for determination of drug concentration in plasma will be assayed by bioanalytical test sites operated by or on behalf of AstraZeneca, using an appropriately validated bioanalytical method. Full details of the analytical method used will be described in a separate Bioanalytical Report.

Drug concentration information that may unblind the study will not be reported to investigative sites or blinded personnel.

Incurred sample reproducibility analysis, if any, will be performed alongside the bioanalysis of the test samples. The results from the evaluation, if performed, will be reported in a separate Bioanalytical Report.

# 8.4.2 Immunogenicity Assessments

Blood samples for determination of ADA in serum will be collected at time points listed in Section 1.3 and assayed by bioanalytical test sites operated by or on behalf of AstraZeneca, using appropriately validated bioanalytical methods. Tiered analyses will be performed to include screening, confirmatory, and titer assay components. Assessment of cross-reactivity to GLP-1 and glucagon may be performed on samples that are confirmed positive for ADA.

ADA samples may also be further tested for characterization of the ADA response. Additional analyses may be conducted on anonymized, individual or pooled immunogenicity samples to further evaluate and validate the analytical method. Any results from such analyses may be reported separately from the CSR.

Samples will be collected, labeled, stored, and shipped as detailed in the Laboratory Manual.

#### 8.4.3 Pharmacodynamics

## 8.5 Human Biological Sample Biomarkers

## 8.5.1 Collection of Mandatory Samples for Biomarker Analysis

Required samples for biomarker research (Section 8.1.5) will be collected from all participants

in this study as specified in the SoA (Section 1.3).

Analysis of biosamples may be performed for safety analytes or for biomarkers or analytes that may play a role in NASH and related conditions including but not limited to their association with disease progression and observed clinical responses to cotadutide. The results of this biomarker research may be reported either in the CSR or as an addendum, or separately in a scientific report or publication. The results of this biomarker research may be pooled with biomarker data from other studies to generate hypotheses to be tested in future research.

# 8.5.2 Collection of Optional Biomarker Samples

Collection of optional samples for biomarker research is also part of this study as specified in the SoA (Section 1.3) and is subject to agreement to optional consent. Optional blood samples will be collected, and analysis may be performed for safety analytes or for biomarkers thought to play a role in NASH and related conditions including, but not limited to, their association with disease progression and observed clinical responses to cotadutide. Optional biomarker samples will be collected according to local regulatory approval.

# 8.6 Optional Genomics Initiative Sample

Collection of optional samples for Genomics Initiative research is also part of this study as specified in the SoA and is subject to agreement in the ICF addendum. A blood sample for DNA isolation will be collected from participants who have consented to participate in the genetic analysis component of the study. Participation is optional. Participants who do not wish to participate in the genetic research may still participate in the study. Refer Appendix D for information regarding the Genomics Initiative genetic sample. Details on processes for collection and shipment and destruction of these samples can be found either in the appendices or in the Laboratory Manual. For storage and destruction of genetic samples refer to Appendix D.

#### 9 STATISTICAL CONSIDERATIONS

# 9.1 Statistical Hypotheses

For the primary safety objective, analyses will compare cotadutide treatment to placebo. The exploratory efficacy analyses will test the null hypotheses of no treatment effect for cotadutide versus placebo in the FAS.

# 9.2 Sample Size Determination

Approximately 7440 participants were originally planned to be screened/enrolled to achieve 1860 randomly assigned to study intervention, including 300 in Part A. However, this study has prematurely stopped randomization as the cotadutide program has been discontinued. The sample size for this study includes approximately 55 randomized participants. The original

sample size calculations for Part A are detailed below.

In Part A, 300 participants were originally to be randomized in a 2:1:2:1 ratio. Approximately 100 participants were planned for each for each dose of cotadutide and 50 participants for each matching placebo group. This sample size was derived with respect to the comparison of each cotadutide group to the pooled placebo group for the proportion of participants with resolution of NASH without worsening of liver fibrosis at Week 48. The sample size would provide > 90% power for the test of each dose versus placebo to detect a difference of 20% in NASH resolution assuming a placebo response rate of 15%. The calculations assumed a 2-sided alpha level of 0.05.

The effects were assumed after any impacts from treatment discontinuation, early withdrawal, missing data imputation, etc. The assumed effect sizes for the histology-based endpoints took into account the PROXYMO interim analysis results as well as the published effects for a GLP-1 receptor agonist (Newsome et al 2021).

Note: "Enrolled" means a participant's, or their legally acceptable representative's, agreement to participate in a clinical study following completion of the informed consent process. Potential participants who are screened for the purpose of determining eligibility for the study but are not randomly assigned/assigned in the study, are considered "screen failures."

# 9.3 Populations for Analyses

The following populations are defined:

Table 14 Populations for Analysis

Population/Analysis set	Description
Enrolled	All participants who sign the ICF.
Randomized	All participants randomized into the study.
FAS	All participants who have been randomized to and received at least one dose of IP.
PP	Subset of FAS population with evaluable post-baseline biopsy after at least 36 weeks of treatment.
Safety	The Safety analysis set consists of all participants who have received at least one dose of IP. Erroneously treated participants (eg, those randomized to treatment A but actually given treatment B) are accounted for in the treatment group with the majority of estimated usage. In all cases, the dose level for analysis will correspond to the randomized dose.
PK	The PK population includes all participants who receive at least 1 dose of study intervention and have at least 1 complete intended PK sample containing detectable cotadutide concentrations.

FAS, full analysis set; ICF, informed consent form; IP, investigational product; PK, pharmacokinetic(s); PP, per protocol

# 9.4 Statistical Analyses

This section is a summary of the planned statistical analyses of the endpoints. A more technical and detailed description of the statistical analyses will be provided in the SAP.

#### 9.4.1 General Considerations

The primary analyses will be of safety. No formal hypothesis testing will be performed. Treatments will be compared in tables using descriptive statistics.

Exploratory efficacy analyses will use nominal 2-sided 5% significance levels (equivalent to nominal 1-sided 2.5% significance levels) unless otherwise stated.

The primary estimand of interest for the histological endpoints will use the treatment policy strategy. The treatment policy approach applies to intercurrent events of treatment discontinuation, deviations from the protocol titration schedule, changes in background medication, liver events, or use of prohibited medication or other protocol deviations. The treatment policy strategy will also be used to handle the intercurrent events for continuous endpoints.

Participants will be analyzed according to their randomized IP assignment and dose, irrespective of the treatment they actually received. Analyses will be performed using the FAS and/or per protocol analysis sets, as appropriate (Table 14). The FAS will include all randomized and treated participants who received at least one dose of IP irrespective of their protocol adherence, addition or modification of background medications, discontinuation of study intervention or switches to alternative medications, and continued participation in the study.

# 9.4.2 Efficacy

The following exploratory endpoints will be analyzed descriptively versus placebo with 95% CIs at the nominal 2-sided alpha 5% level:

- Resolution of NASH at Week 48 without worsening of fibrosis
- Improvement in fibrosis at Week 48 without worsening of NASH
- Resolution of NASH and improvement in fibrosis at Week 48
- Improvement in fibrosis by at least one stage at Week 48
- Change from baseline in triglycerides, LDL cholesterol, HDL cholesterol, non-HDL cholesterol, total cholesterol, and HbA1c through Week 48

Additional exploratory endpoints and their analyses will be detailed in the SAP.

The binary endpoint(s) will be analyzed using a Cochran-Mantel-Haenszel test with stratification by T2DM presence and F2/F3 fibrosis stages. The treatment effects will be summarized by the difference in proportions, 95% CI, and p-value. For the exploratory analysis of binary histological endpoints using FAS, participants with no liver outcome and missing histology data due to any reason may be imputed as non-responders.

Continuous endpoints (absolute change in body weight, change in HbA1c, percent change in triglycerides) will be analyzed using Analysis of Covariance models, adjusting for baseline value, presence of T2DM, and fibrosis stage (F2/F3). For the primary analyses of these endpoints, missing data will be imputed via multiple imputations.

## **9.4.3 Safety**

Safety analyses will be performed using the safety analysis set. Safety data will be presented using descriptive statistics unless otherwise specified and will not be formally tested.

Safety events and findings will be summarized by treatment group. Erroneously treated participants (eg, those randomized to treatment A but actually given treatment B) are accounted for in the treatment group with the majority estimated usage. The majority estimated usage will be determined based on which treatment had more kits dispensed (not including kits returned unused). In the case of a tie, the randomized treatment will be used for safety analyses. In all cases, the dose group will be the same as randomized dose level.

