### 3 OBJECTIVES, ENDPOINTS, AND ESTIMANDS

# 3.1 Objectives and Endpoints: Part A

Table 8 Objectives and Endpoints: Part A

Objectives	Endpoints
Primary/Safety	
To evaluate the safety and tolerability of cotadutide as compared with placebo in participants with non-cirrhotic NASH with fibrosis	Safety and tolerability will be evaluated in terms of AEs, vital signs, clinical and laboratory assessments, and ECG. Assessments related to AEs cover:  Occurrence/Frequency Relationship to IP as assessed by the investigator Intensity Seriousness Death AEs leading to discontinuation of IP AEs leading to dose reduction of IP AEs of special interest Adjudicated CV events including MACE, selected liver events, diabetic ketoacidosis, pancreatitis, pancreatic carcinoma, and thyroid carcinoma
	Vital signs parameters include SBP, DBP, and pulse.
	Assessments cover:
	Observed value

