#### **Adverse Events**

Adverse events will be coded using the most recent version of the MedDRA that will have been released for execution at AstraZeneca. AEs will be presented for each treatment group by SOC and/or Preferred Term covering number and percentage of participants reporting at least one event and number of events where appropriate. Exposure-adjusted incidence rates may be provided as appropriate. Only treatment-emergent AEs will be summarized.

An overview of AEs will present the number and percentage of participants with any AE, AEs with outcome of death, serious AEs, AEs leading to discontinuation of IP, and AEs leading to dose reduction of IP for each treatment group.

Separate AE tables will be provided taking into consideration the relationship as assessed by the investigator, maximum intensity, seriousness, death and events leading to discontinuation of IP as well as AESIs.

In accordance with the requirements of the FDA, a separate table will present non-serious AEs occurring in more than 5% of participants in any treatment group.

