## 4.2.3.4 Primary Analysis of Other Endpoints

Unless otherwise indicated, analyses of tertiary/exploratory histological endpoints and continuous exploratory endpoints at Week 48 will include both on- and off-treatment measurements while analyses of endpoints at multiple timepoints through Week 48 will only include on-treatment measurements. The treatment effect for binary exploratory endpoints will be analyzed by the Cochran-Mantel-Haenszel (CMH) test, stratified for T2DM presence and F2/F3 fibrosis stages. The difference in proportion (unstratified response difference) with Miettinen-Nurminen (ie, score-based; without stratification) 95% confidence interval, and nominal p-value from CMH chi-square test will be provided.

Continuous endpoints summarized for a single post-baseline timepoint (Week 48) will be analyzed using ANCOVA with baseline, baseline T2DM status, baseline fibrosis stage, and treatment as independent variables, using multiple imputation. If an issue is encountered for fitting an ANCOVA model (eg, collinearity with intercept), a simplified model may be used. For analysis of (absolute) change from baseline, endpoints will be analyzed without transformation and LSMEAN change from baseline by treatment; the treatment effect as the LSMD will be reported as point estimates and 95% confidence intervals with p-values provided for treatment effect. For analysis of percent change from baseline, ANCOVA will be performed using log-transformed values. Point estimates and 95% confidence intervals of percent change from baseline by treatment and ratio change from baseline will be reported with a nominal p-value for treatment effect (Section 4.2.3.2). Rubin's rules (Rubin 1987) will be used to pool LSMEAN and LSMD values and associated standard errors across multiply imputed datasets and will provide the reported estimates and p-values. The following variables will be log-transformed: ALT, AST, APRI, triglycerides, PRO-C3, FIB-4, FPG, (total and high molecular weight) adiponectin, and C-peptide. Other variables may be log-transformed if required.

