# 4.5 Safety Analyses

Safety analyses include exposure, AEs, clinical laboratory results, vital signs, and ECGs. Safety events and findings will be summarized by treatment group. Erroneously treated participants (eg, those randomized to treatment A but actually given treatment B) are accounted for in the treatment group with the majority estimated usage. The majority estimated usage will be determined based on which treatment had more kits dispensed (not including kits returned unused). In the case of a tie, the randomized treatment will be used for safety analyses. In all cases, the dose group will be the same as randomized dose level.

Tables are provided for the safety set and listings are provided for all participants or the safety set depending on the availability of data.

Laboratory, vital sign, and ECG interval abnormalities will be considered treatment emergent if collected after the first dose and if the result is numerically more extreme than baseline – ie, the result is lower than baseline for low abnormalities and higher than baseline for high abnormalities. In cases of a missing baseline value (and for all random glucose abnormalities, since there is no planned baseline), any post-baseline value meeting the post-baseline criteria will be considered to be an abnormality. Treatment-emergent increase in urinalysis defined as change from negative/trace at baseline to ++, +++, or ++++ at any visit after baseline or an increase of at least ++.

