#### 4.5.2.2 Presentation

AEs will be summarized for each treatment group. The AE tables will be based on the safety analysis set. Summary tables will include all on-study AEs. Select AE and AESI summaries will be repeated for all on-treatment events as appropriate.

Summary tables are listed below.

An overview table will contain summaries of the number and percentage of participants with the following:

- Any AE
- Any AE considered related to IP
- Any AE leading to death
- Any SAE
- Any AE leading to discontinuation of IP

- Any AE leading to a reduction of IP dose
- Any AE leading to withdrawal from the study

The following summary tables will be presented by SOC and PT:

- Any AE
- Any AE considered related to IP
- Any AE leading to death
- Any SAE
- Any AE leading to discontinuation of IP
- Any AE leading to a reduction of IP dose
- Any AE leading to withdrawal from the study
- The number and percentage of participants with any AEs by maximum reported intensity

On-study AESIs will be summarized as number and percentage of participants with the following:

- Any AESI
- Each specific AESI will also be summarized, overall and by maximum intensity
- Each specific AESI will be summarized by SOC and PT
- Select AESI summaries will be repeated for all on-treatment events as appropriate

Adjudicated events (separate on-study and on-treatment analyses) will be summarized as number and percentage of participants with the following:

- Any liver event (hepatic decompensation, clinical cirrhosis, DILI, hepatocellular carcinoma, or death from any cause)
- Events of hepatic decompensation
  - Clinically apparent ascites requiring treatment
  - Complication of ascites (eg, spontaneous bacterial peritonitis, diuretic-resistant ascites [refractory ascites], hepato-pleural effusion)
  - Hepatic encephalopathy of Grade 2 or above (according to the West Haven criteria) requiring treatment
  - Portal hypertension-related upper gastrointestinal bleeding identified by endoscopy and requiring hospitalization, including events of bleeding from esophageal varices, gastric varices, and portal hypertensive gastropathy
- Clinical cirrhosis
- DILI
- Hepatocellular carcinoma

- Death by any cause
- 3-point MACE
- 5-point MACE
- CV death
- Cardiac ischemic events Myocardial Infarction (non-fatal)
- Cardiac ischemic events Myocardial Infarction (any)
- Cerebrovascular events- Stroke (non-fatal)
- Cerebrovascular events- Stroke (any)

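### The primary AE comparison with placebo is planned as counts and percentages per group, with no risk difference or interval, although the exploratory binary efficacy endpoints get both

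*Protocol*

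**What the plan says.** The primary objective in Protocol 3.1 is comparative: "To evaluate the safety and tolerability of cotadutide as compared with placebo in participants with non-cirrhotic NASH with fibrosis". Protocol 9.1 repeats this: "For the primary safety objective, analyses will compare cotadutide treatment to placebo".

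Protocol 9.4.1 gives the form of the comparison: "Treatments will be compared in tables using descriptive statistics". Protocol 9.4.3 adds: "Safety data will be presented using descriptive statistics unless otherwise specified and will not be formally tested". For AEs, the protocol plans tables by treatment group, "covering number and percentage of participants reporting at least one event and number of events where appropriate". Exposure-adjusted rates are optional.

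The SAP follows this. Section 4.5 states: "Safety events and findings will be summarized by treatment group". Section 4.5.2.2 states: "An overview table will contain summaries of the number and percentage of participants with the following". The AESI and adjudicated-event summaries in the same section are also number and percentage. Further adjudicated-event analyses are left open, to be done if required. No AE output names a risk difference, a ratio or an interval.

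For the exploratory binary efficacy endpoints, SAP 4.2.3.4 specifies: "The difference in proportion (unstratified response difference) with Miettinen-Nurminen", followed by a 95% confidence interval and a nominal p-value.

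**The concern.** After the amendment, safety is the primary question and efficacy is exploratory. Yet the exploratory binary endpoints get an estimated contrast with its precision, and the primary AE comparison does not.

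At about 18 participants per group, bare percentages can mislead in two directions. A row with no events may be taken as reassurance when the data are compatible with a substantial event rate. A visible gap may be taken as a drug effect, or dismissed, when its size alone does not say which reading the data support. Declining to test is reasonable for a trial cut from 300 to about 55 participants, but it does not require leaving out estimation. Protocol 9.4.2 itself treats 95% CIs as part of a descriptive analysis of efficacy.

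**Working it through.** **The plan's own figure.** The only precision-related figure in the documents is the original Part A power: more than 90% for 35% v 15% NASH resolution, 100 per dose v 100 pooled placebo, two-sided 0.05 (Protocol 9.2).
- Null SE = √(2 × 0.25 × 0.75 / 100) = 0.0612. Alternative SE = √(0.15 × 0.85/100 + 0.35 × 0.65/100) = 0.0596.
- Power = Φ[(0.20 − 1.96 × 0.0612)/0.0596] = Φ(1.34) = 91.0%.

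It reproduces, but it concerns an efficacy endpoint with 300 participants. The documents give no precision figure for safety at about 55.

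**Group sizes.** 55 × 2/6 = 18.3 per cotadutide dose and 55 × 1/6 = 9.2 per placebo arm. Pooled placebo is 18.3, and both doses combined are 36.7. I use 18, 9, 18 and 37, and assume that nearly all randomized participants are dosed.

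**Zero counts.** The exact two-sided 95% upper limit for 0/n is 1 − 0.025^(1/n).
- 0/18: 18.5%
- 0/37 (doses combined): 9.5%
- 0/9 (one unpooled placebo arm): 33.6%

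The chance of seeing no event at all in 18 participants is 0.90^18 = 15.0% when the true rate is 10%, and 0.95^18 = 39.7% when it is 5%.

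**Differences.** The unstratified Miettinen-Nurminen limits are the values δ that solve (p̂₁ − p̂₂ − δ) / √{[p̃₁(1−p̃₁)/n₁ + p̃₂(1−p̃₂)/n₂] × N/(N−1)} = ±1.96. Here p̃₁ and p̃₂ are the maximum likelihood estimates under p₁ − p₂ = δ, and N = n₁ + n₂. The event counts are illustrations and do not come from the documents.

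| Cotadutide v placebo | Difference (points) | 95% CI (points) |
|---|---|---|
| 0/18 v 0/18 | 0 | −18.0 to 18.0 |
| 3/18 v 0/18 | 16.7 | −2.9 to 39.6 |
| 6/18 v 1/18 | 27.8 | 1.8 to 52.4 |
| 9/18 v 4/18 | 27.8 | −4.1 to 54.8 |
| 9/18 v 2/9 (unpooled) | 27.8 | −12.5 to 57.3 |

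The last three rows show the same 27.8-point gap. The interval excludes zero in one and includes it in the other two, depending on the event rate and on whether placebo is pooled. Subtracting two percentages does not show this.

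**The case against.** The strongest reply is that the plan is consistent and deliberate. It says that the comparison is made side by side in tables, without testing, and it says so in both documents. A randomized placebo column next to each dose is a comparison. This stands: a reader might infer that Protocol 9.1 contradicts 9.4.3, but the documents do not support that. The point is an omission of precision.

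A reader might also infer that the AE tables cannot be interpreted. They can. They give n and %, so anyone can derive the difference and its interval, as done above. What is missing is a planned display of the uncertainty.

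A third inference would be that the whole primary objective lacks any statement of precision. That is too broad. SBP, ALT and AST receive model-based estimates with 95% CIs as exploratory endpoints (SAP 4.2.3.1 and 4.2.3.4), and the continuous safety summaries report SDs. The gap concerns AE, AESI and adjudicated-event outputs.

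The SAP amendment history records that optional contrast measures for safety, such as risk difference, were introduced in November 2022. That entry describes superseded text, so their absence from the current SAP 4.5 is not an error.

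Finally, intervals on every row would be excessive. The overview has 7 rows, the AESI summary 16 (15 named plus any) and the adjudicated events 23. With three contrasts that is 46 × 3 = 138 unadjusted intervals, many on nearly empty rows, and some readers would treat them as tests. This stands and limits the fix.

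**Conclusion.** The point holds as a low-cost improvement to the AE outputs. The primary AE comparison is planned without an estimate of the difference or its uncertainty, and the SAP already specifies a suitable method for less important endpoints. No planned number is wrong and no analysis is invalid.

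The size is material at this sample. No events in 18 is compatible with a true rate up to 18.5%, and a gap of nearly 28 points may or may not exclude zero.

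The conclusion rests on three assumptions. About 55 participants are randomized 2:1:2:1. The event counts are illustrative. The placebo arms are pooled to about 18, which assumes similar AE rates under the two placebo titration schedules. The safety sections refer only to treatment group and do not say whether placebo is pooled. Unpooled, each placebo arm has about 9 and the intervals are wider.

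**What to change.** In SAP 4.5.2.2:
- State that the two placebo arms are pooled for safety contrasts.
- In the AE overview table and in the any-AESI and individual-AESI rows, add the unstratified risk difference with a Miettinen-Nurminen 95% CI for each dose v pooled placebo and for both doses combined v pooled placebo.
- Label these descriptive, with no p-values and no multiplicity claim.
- Leave the SOC/PT tables and the rare adjudicated-event rows as counts and percentages.

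This is (7 + 16) × 3 = 69 intervals for the on-study tables. The ban on formal testing in Protocol 9.4.3 is untouched, because that sentence does not exclude an interval. The cost is SAP wording and some table columns, using a method already specified for efficacy. The downside is wide, unadjusted intervals, slightly larger tables and some residual risk that an interval excluding zero is read as a test.
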